Video training supplementation to reduce the risk of central venous catheter infection in patients discharged on home parenteral nutrition

Principal Investigator: [name]
Co-Investigators: [name]., [name]

Background

Home parenteral nutrition (PN) is an alternative form of nutrition in patients in whom enteral nutrition is infeasible or insufficient in the long term.^{1,2} Home PN improves the quality of patients' life and consequently also the course of the underlying disease, with optimization of nutrition status.² A study conducted in Australia found that home PN had a positive impact on the daily living of patients.³ In recent years, more emphasis has been placed on delivering parenteral nutrition to patients at home, which may improve patient care and reduce costs.⁴ Thus, more patients rely on TPN for lifesaving nutrition support. There were an estimated 20,883 adult patients receiving home PN in 2013 based on data from Medicare and Medicaid Services.⁵ The use of home PN has increased in recent years in adult patients.⁶⁻⁹ Although comprehensive data is lacking in the United States, there is a trend of increasing home PN use across many countries, including UK, Canada, and Spain.^{8,10}

Studies have shown that patients receiving total parenteral nutrition (TPN) are at higher risk for bloodstream infections compared to other patients with chronic infusion needs¹⁻¹⁴. Increased parenteral caloric intake is an independent risk factor for bloodstream infection in patients receiving TPN. A prospective study in 87 critically ill patients showed that patients who had catheter related bloodstream infection (CRBSI) received more parenteral calories (36 kcal/kg/day versus 31 kcal/kg/day, $P = 0.003$).^{11,12} Catheter-related bloodstream infection is a major cause of mortality and morbidity in patients receiving TPN.^{13,14} Therefore, it is important to maintain safe vascular access to prevent life-threatening complications.

Fortunately, there are interventions that reduce risk for bloodstream infection in home TPN. In a retrospective study, chlorhexidine gluconate transparent antimicrobial dressing reduced CRBSI from eight cases to zero case in 12 months.¹⁵ Another research study found that patients with parenteral nutrition who are managed by a dedicated nutrition support team are less likely to develop CRBSI at 24 months than a variety of physicians (1.3% vs 26.2%).¹ More importantly, patient engagement and education program has been proven feasible and potentially effective. An oncology unit in Denmark developed an education program for 42 out of 82 randomized patients with tunneled central vein catheters. 88% of the 42 patients completed the training, and the 42 patients had 50% less CRBSI in a five-month period.¹⁶ A group in MD Anderson Cancer Center designed an in-person and video education program for central catheter care. After 1 year, 95% of the participating patients caring for the catheters at home, and 97% of them reported confidence and satisfaction in catheter care.¹⁷

We developed an education video addressing the aseptic techniques to safely handle central catheters at home for TPN use. It will be hosted in a mobile app with a secure link. Our primary aim is to assess the effect of the video training supplementation prior to discharge on the rate of CRBSI over a 12-month period of time. Our secondary aims are

to assess the patient's comfort level when handling catheters for patients newly initiated home TPN.

Hypothesis

We hypothesize that 1) the video will improve rates of CRBSI compared to a control group receiving written catheter instructions; 2) the video will improve patients' comfort level with handling central catheters; 3) patients will find the video easy to use.

Participants

Inpatient adult patients who are discharged home for the first time on home TPN will be approached for consent and inclusion in this prospective study design.

Study duration

24 months

Methodology

Inclusion Criteria

1. Patient will be discharged to start TPN at home.
2. Age ≥ 18 yrs.
3. Ability to understand and sign written consent form.
4. English-speaking patients.
5. Patients who are willing to self-administer TPN at home.

Exclusion Criteria

1. Patients without consent
2. Patients who have been on home TPN prior to the index admission at any time in the past
3. Non-English-speaking patients
4. Patients who will not self-administer TPN.

During initial screening and recruitment, it will be necessary to acquire potential participants' names and medical record numbers. Medical record numbers will be used to confirm the patients' diagnosis and home TPN usage by reviewing electronic medical records. Names are necessary to obtain permission to approach the patients from the patients' physicians. This information will be stored electronically in a password-protected file on a computer in room M-421. After screening and recruitment, patient names will be replaced anonymous study I.D. numbers. For patients choosing not to participate in the study, medical record numbers will also be deleted, and standard of care will be continued.

Following consent, each subject will be asked to complete a "TPN Central Catheter Self-Care Questionnaire" (Appendix 1). The primary role of the enrollment questionnaire is to assess for baseline comfort level to manipulate a central catheter at home. In addition, following enrollment, electronic chart review will be performed to assess for clinical and laboratory variables within three months of enrollment (complete blood count, renal function, liver function studies, type of catheter placement, extent and duration of disease and comorbid conditions [Charlson score]).

All enrolled patients will receive baseline in-person hands-on training for catheter use. Then the patients will be randomly assigned to the control group (written instructions) or the intervention group (provided video link).

A baseline entry questionnaire will be administered to assess the patients' comfort level for central catheter use and indications for PN. Each subject will use their study I.D. in lieu of their name. Then patients in the intervention group will be given a link to the educational video, which they can access as many times as they prefer.

Six weeks following enrollment, study participants will be asked to complete a second "TPN Central Catheter Teaching and Self-Care Questionnaire" (Appendix 2) via an email or secure text link generated from patient.iq. to reassess participants' comfort level of catheter self-care.

Six months following enrollment, study participants will be asked to complete a "Conclusion of Study Questionnaire" (Appendix 3) via an email or secure text link generated from patient.iq. The role of the concluding questionnaire is to assess for subjective reports of their confidence and comfort level in central line self-care.

If a subject fails to respond to these electronic questionnaires, the IRB-approved study staff will approach he/she during a standard GI Nutrition follow-up clinic visit to obtain answers for the questionnaire via a secure link on a tablet device.

The follow-up period will not exceed one year beyond the inclusion date. At the end of one year, the IRB-approved study staff will gather clinical information from the electronic medical record to determine if each subject has had a CRBSI event. Per CDC, CRBSI is defined as a laboratory confirmed infection where a Central Venous Catheter (CVC) is in place for over 2 calendar days prior to a positive culture and is also in place the day of or day prior to culture. And not deemed as a result from contamination by the primary hospital team at the time of the treatment.

The subjects will undergo weekly laboratory tests (complete blood count, electrolytes, liver function, and kidney function) as part of their routine standard of care to ensure the TPN formula is up to date and meets subjects' nutritional and metabolic needs. If a subject seeks care outside of UChicago, subject's UChicago care team members will obtain permission to have the health information released to UChicago, as part of the subject's standard of care. If patient wishes to transfer care of their TPN and CVC permanently to another institution, then their participation in this study will be terminated.

Additionally, subjects will be followed-up weekly via phone by their care team at UChicago as part of subjects' routine standard of care to ensure safe use of CVC and TPN infusions.

Study Schema

Assessment/Procedure	Visit 1	Visit 2	Visit 3	Visit 4
Informed consent	X			
Data collection: Demography and medical history	X			
Randomization	X			

Watch video/ follow written instructions	X	X	X	
Complete questionnaire	X	X	X	
Review medical, surgical, and hospitalization records for CRBI evaluation				X

Location

Patients will be consented at the University of Chicago's Center for Care and Discovery and Mitchell Hospital. All obtained data will be stored in a password protected computer or a locked drawer in the research office in M-421.

Potential risks and benefits

There is a minor risk of loss of confidentiality with participation in this study since subject identifiers will be collected. However, all study data will be recorded in a database where names and medical record numbers will be removed and replaced with a study I.D. Only the study staff will have access to the key which links the study code to the subject's identity.

Patients may receive no direct benefit from participation in this study, but it is anticipated they will benefit from improve catheter self-care techniques, and an improved physicians' understanding of catheter associated bloodstream infections.

Special Precautions

No specimens will be collected during this study. Standard precautions will be provided during all patient encounters and clinical care.

Special precautions will be taken by research staff to ensure confidentiality. All data review will be performed electronically on a password-protected computer in a locked and limited access area.

Data will be coded in case the study team needs to go back and re-check data or look into abnormalities. Subjects are assigned a unique study code in place of their name and MRN. Only the study staff will be able to link data with subjects' identifiable information. Upon termination of the study, the coding link will be destroyed, leaving only completely de-identified data.

Experimental controls and use of placebos

N/A

Number of experimental subjects

One hundred (100) subjects will be included in the study.

Data Analysis

The rate of CRBSI will be determined. Risk factors for the CRBSI will be assessed in univariable and multivariable analysis based on pre-defined clinical and subjective risk factors.

Statistical justification

The rationale for the number of subjects is as follows. With 30% rate of bloodstream infection, and a 70% power and 95% confidence interval, the total sample size required would be 93 patients in order to see a reduction in the rate of bloodstream infection. Suppose a 10% rate for loss to follow-up, the total subjects will be 100 patients.

At the end of the study, the rate of CRBSI will be calculated and compared between the TPN video group and the control group using an unpaired Student's T test. The frequency of TPN video use will be reported as quantitative data based on discrete values. The comfort level of CVC handling will be aggregated, and the mean value will be compared between the video group and the control group using an unpaired Student's T test.

Informed Consent

Written consent will be obtained in standard fashion using an IRB-approved consent form. The patient will be approached by the PI, Co-I, or a trained study staff member. All ethnic populations will be eligible and recruited. The study will be explained in detail during a standard-of-care inpatient GI nutrition consultation visit, all patient questions will be answered and sufficient time will be allowed for the subject to make a decision regarding participation. The original signed consent form will be stored in a locked drawer in M-421.

Patients that do not agree to participate in the study will continue to receive standard-of-care treatment. At the time of consent, patients will also be informed that they are free to withdraw from the study at any time they wish.

Confidentiality

During initial data collection, patient names will be used. However, after entering the selected data values into our study database, the medical record numbers and names will be stripped from the information to insure confidentiality. Unique, study-specific identifiers will be assigned to individual subjects' data. Manipulation of data and reporting results will be performed in aggregate fashion and in no way will identify individual subjects. In addition, all data and any information that has specific medical record numbers recorded will be maintained in a secure location (M-421) and locked cabinet or password protected database. Only the P.I., Co-I's and IRB-approved study staff will have access to these identifiers.

Recruiting methods

Patients will be referred from all inpatient primary services at the University of Chicago for eligibility of home TPN, who will grant permission for us to approach their patients for recruitment to this study.

A rationale for excluding women, minorities and/or children from participation

N/A

2023.10.16

Bibliographic References

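### Patients are randomised in hospital and the CRBSI count has no post-discharge condition, so index-stay line infections would count as primary events and weaken the video effect

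*Combined protocol and SAP*

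**What the plan says.** **Place of inclusion.** The first inclusion criterion looks ahead to discharge: "Patient will be discharged to start TPN at home". Under Informed Consent, "The study will be explained in detail during a standard-of-care inpatient GI nutrition consultation visit". The Study Schema puts consent and randomisation at the same Visit 1.

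**Window.** The primary aim, at the end of Background, is the effect of "video training supplementation prior to discharge on the rate of CRBSI over a 12-month period of time". No start date is given for those 12 months. Methodology adds "The follow-up period will not exceed one year beyond the inclusion date". The questionnaires are also timed from enrolment.

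**Event.** At one year staff will "gather clinical information from the electronic medical record to determine if each subject has had a CRBSI event". The definition requires that a central line "is in place for over 2 calendar days prior to a positive culture" and is still in place at, or the day before, the culture. The only exclusion is a result that the treating team judged to be contamination. No condition refers to discharge or home onset, and index-admission events are not excluded.

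**Target of the video.** Background describes it as teaching aseptic handling of the catheter at home.

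**The concern.** Between randomisation and discharge the patient is still in hospital and has not begun home self-care, which is what the video is meant to improve. An infection in that interval says almost nothing about the video, yet a chart reviewer following the text would record it as a primary event.

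Events that the intervention cannot modify add roughly equal counts to both arms. The ratio is pulled towards 1, the difference shrinks a little and variance rises. The plan targets only 70% power, so it has little to spare. Reviewers also have no rule for index-stay cultures and could classify similar cases differently.

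**Working it through.** **Inputs from the documents.** Control rate 30%, 70% power, 95% confidence, 100 patients with 10% loss (Statistical justification). That leaves 100 × 0.90 = 90, or 45 per arm.

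**Assumptions.** 1:1 allocation; two-sided 5% test; video-arm risk 15%; interval d from inclusion to discharge; inpatient hazard k times the home control hazard, equal in both arms. The documents give none of these. The 15% halves the control rate, in line with the halving reported for the randomised education programme described in Background.

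**The plan's own figure.** The stated total of 93 cannot be reproduced, because no video-arm rate is given. Back-solving the pooled two-sided formula gives 30% against about 9.6%; 30% against 10% gives 98. A second scenario below therefore uses 10%.

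**Model.** With constant hazards over a 365-day window from inclusion:

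- λc = −ln(0.70)/365 = 0.000977 per day; λv = −ln(0.85)/365 = 0.000445 per day
- Control risk = 1 − exp{−[λc·k·d + λc(365 − d)]}
- Video risk = 1 − exp{−[λc·k·d + λv(365 − d)]}

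Example, d = 14 and k = 3:

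- control: 1 − exp{−(0.0410 + 0.3430)} = 31.9%
- video: 1 − exp{−(0.0410 + 0.1563)} = 17.9%
- risk ratio 0.56

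Power uses the pooled two-proportion z-test with n = 45 per arm, p̄ the mean of the two risks and Δ their difference: Φ{[Δ − 1.96√(2p̄(1 − p̄)/n)] / √([pc(1 − pc) + pv(1 − pv)]/n)}. With no gap this is Φ{(0.150 − 0.1725)/0.0866} = 39.7%.

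| d (days) | k | Control | Video | Difference (points) | Risk ratio | Power |
|---|---|---|---|---|---|---|
| 0 | – | 30.0% | 15.0% | 15.0 | 0.50 | 39.7% |
| 2 | 1 | 30.0% | 15.1% | 14.9 | 0.50 | 39.3% |
| 2 | 5 | 30.5% | 15.8% | 14.8 | 0.52 | 38.2% |
| 3 | 5 | 30.8% | 16.1% | 14.7 | 0.52 | 37.4% |
| 7 | 1 | 30.0% | 15.3% | 14.7 | 0.51 | 38.2% |
| 7 | 5 | 31.9% | 17.6% | 14.3 | 0.55 | 34.6% |
| 14 | 1 | 30.0% | 15.6% | 14.4 | 0.52 | 36.7% |
| 14 | 3 | 31.9% | 17.9% | 14.0 | 0.56 | 33.3% |
| 14 | 5 | 33.7% | 20.1% | 13.6 | 0.60 | 30.5% |

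Power falls by 0.4 to 9.2 points. Exact enumeration of the same test gives 41.6% with no gap and 31.8% at d = 14, k = 5, a loss of 9.8 points.

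**Second scenario, 30% against 10%.** Let q be the pre-discharge risk in both arms, so that each observed risk is q + (1 − q)p. At 46.5 per arm (93/2), power is 67.9% at q = 0, 65.7% at q = 1% and 57.5% at q = 5%. The risk ratio moves from 0.33 to 0.36 and 0.43. For scale, a 7-day gap gives q = 0.7% at k = 1 and 3.4% at k = 5.

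**The case against.** **The follow-up sentence sets an end, not a start.** This is correct. A reader might infer that the plan expressly starts counting at inclusion; it does not. The trial title and primary aim, which concern patients discharged on home nutrition, fit a post-discharge reading. Even so, inclusion is the only anchor given and nothing excludes index-stay events, so the literal reading counts them.

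**The size is assumed.** This also stands. Patients are approached when home nutrition is already planned, so a gap of a few days is plausible and the cost is then 1 to 2 points of power. The larger figures need both a long gap and a raised inpatient hazard.

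**The ratio exaggerates.** Partly right. The planned t test compares rates on the difference scale, where 15.0 points becomes 13.6 in the worst case shown.

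**Counting from randomisation is standard intention-to-treat practice.** It is, which is why that count should be retained. It does not settle which count best answers a question about handling at home.

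**First days at home.** A reader might infer that infections just after discharge also belong to the hospital, by the plan's own 2-day rule. The documents do not support this. That rule concerns how long the catheter was in place before the culture, not where the infection began, and video patients have access to the video from Visit 1.

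**The contamination exclusion might remove hospital-caused infections.** Its natural meaning is a contaminated culture. If more was intended, the sentence needs rewording.

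**Conclusion.** The point holds as a definitional gap with a modest, conditional cost. Read as written, a CRBSI between inpatient randomisation and discharge is a primary event that home self-care could not have prevented. With 30% against 15%, the risk ratio becomes 0.50–0.52 for a gap of 2 to 3 days and 0.52–0.60 for 14 days, and the power loss at 45 per arm runs from under 1 point to about 10. These figures rest on the assumed gap, hazard multiple and video-arm risk, with constant hazards.

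A reader might go further and infer that the comparison is biased in favour of the video, or invalid. The documents do not support that: randomisation balances these events in expectation, so the effect is drawn towards the null. This is a worthwhile, inexpensive improvement rather than a fatal flaw.

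**What to change.** 1. Define the primary event as a CRBSI with a positive culture after index discharge.
2. State the end of the window: either keep the existing cap of one year from inclusion, which shortens home time by the remaining stay, or amend the cap so that 12 months run from discharge.
3. Analyse all randomised patients in their assigned arms. State in advance how patients never discharged on TPN are counted, and how those with a pre-discharge CRBSI are handled afterwards.
4. Report pre-discharge CRBSI by arm, and give the count from randomisation as a sensitivity analysis.
5. If an attribution rule for the first days at home is wanted, label it as new and use it only as a sensitivity analysis.
6. Clarify that the contamination exclusion refers to cultures.

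**Cost.** Mostly endpoint wording. Discharge and culture dates should be in the records already under review. Moving the cap would be a protocol amendment with slightly longer follow-up. The small downside is that the window opens after randomisation, which item 4 covers. Line handling by staff during later readmissions is not addressed and would need its own onset rule.

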Appendix 2: Central Catheter Teaching and Self-Care Follow-up Questionnaire

Name: _____ Subject ID: _____
 Date: _____ Email: _____

1) What are the cycle hours of your PN (parenteral nutrition)? _____ hours

2)

	Yes	No
Do you currently have an ostomy?		
Do you currently have a fistula anywhere in your body?		
Do you use any other IV medications through the catheter?		

If yes, what IV medications?

3) How comfortable do you feel about using your central venous catheter?

- Very uncomfortable
- Somewhat uncomfortable
- Neutral
- Somewhat comfortable
- Very comfortable

4) How do you find the TPN education material?

- Very confusing
- A little confusing and not as helpful
- The information is clear, but it had no effect on my self-care practice
- Somewhat helpful
- Very helpful

5) How often do you watch the TPN educational material on average?

- I have not watched the video since discharge
- Less than once a week
- 1-2 times a week
- 3-6 times a week
- Daily or more

**Appendix 3: Central Catheter Teaching and Self-Care Conclusion
Questionnaire**

Name: _____ Subject ID: _____
Date: _____ Email: _____

1) What are the cycle hours of your PN (parenteral nutrition)? _____ hours

2)

	Yes	No
Do you currently have an ostomy?		
Do you currently have a fistula anywhere in your body?		
Do you use any other IV medications through the catheter?		

If yes, what IV medications?

3) How comfortable do you feel about using your central venous catheter?

- Very uncomfortable
- Somewhat uncomfortable
- Neutral
- Somewhat comfortable
- Very comfortable

4) How do you find the TPN education material?

- Very confusing
- A little confusing and not as helpful
- The information is clear, but it had no effect on my self-care practice
- Somewhat helpful
- Very helpful

5) How often do you watch the education material on average?

- I have not watched the video since discharge
- Less than once a week
- 1-2 times a week
- 3-6 times a week
- Daily or more

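### Nothing in the protocol keeps the study arm from the staff who decide, from the chart, whether each patient had a CRBSI

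*Combined protocol and SAP*

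**What the plan says.** The combined protocol and SAP sets out the endpoint under Methodology. At one year, "the IRB-approved study staff will gather clinical information from the electronic medical record to determine if each subject has had a CRBSI event". The definition begins with laboratory and catheter-time criteria ("CRBSI is defined as a laboratory confirmed infection where a Central Venous Catheter (CVC) is in place for over 2 calendar days" before a positive culture, and in place on the day of the culture or the day before). It then requires that the infection was "not deemed as a result from contamination by the primary hospital team at the time of the treatment".

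Other statements bear on who might know the arm:

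- Methodology: one arm receives written instructions and the other a link to the video. If a patient does not answer the electronic questionnaires, "the IRB-approved study staff will approach he/she during a standard GI Nutrition follow-up clinic visit" and obtain the answers on a tablet.
- Appendices 2 and 3: the item on use of the education material includes the answer "I have not watched the video since discharge".
- Potential risks and benefits: "Only the study staff will have access to the key which links the study code to the subject's identity".
- Background: the investigators developed the video. Hypothesis: they expect it to improve CRBSI rates.

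No section mentions masking of outcome assessment, an independent assessor, adjudication, or where the allocation list is kept.

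**The concern.** Patients cannot be masked to a video link or a leaflet, so masking of the outcome review is the main protection left, and the protocol is silent on it. Four steps leave room for judgement:

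- finding a possible event in a year of records;
- confirming that the catheter-day criteria are met;
- interpreting records released by other institutions;
- deciding what to do when the treating team's contamination view is missing or unclear, for which no rule is given.

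If the abstractor knows the arm, the search may be less thorough, or an unclear note read more leniently, in one arm. Few events are expected, so a small number of such decisions can matter. Once charts have been read with the arm known, no analysis can undo it.

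**Working it through.** **Inputs.** From Statistical justification: 30% infection rate, 70% power, 95% confidence (read as two-sided α = 0.05), 93 patients required, 10% loss, 100 enrolled, unpaired Student's t test. The allocation ratio is not stated, so 1:1 is assumed. The video-arm rate is not stated, so 10%, 15% and 20% are used as a range.

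**Step 1: the plan's own 93.** It cannot be reproduced from the stated inputs, because the effect is missing. Back-solving with the unpooled formula n per arm = (z₀.₉₇₅ + z₀.₇₀)² × [p₁(1−p₁) + p₂(1−p₂)] / (p₁−p₂)²:

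- 30% v 10%: (1.960 + 0.524)² × (0.21 + 0.09) / 0.04 = 6.172 × 0.30 / 0.04 = 46.29 per arm, 92.6 in total, so 93.
- 30% v 15%: 6.172 × 0.3375 / 0.0225 = 92.58 per arm, about 185 in total.

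So 10% fits the stated total and a halving does not, but 10% remains an inference.

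**Step 2: expected events.** 100 × 0.90 = 90, or 45 per arm. Control: 45 × 0.30 = 13.5. Video: 4.5, 6.75 or 9 at 10%, 15% or 20%. The total is 18 to 22.5 events.

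**Step 3: the planned test on 0/1 data.** t = (p₁−p₂) / √[s²(1/n₁ + 1/n₂)], where s² = [n₁p₁(1−p₁) + n₂p₂(1−p₂)] / (n₁+n₂−2). For 14 v 7 of 45: s² = (9.644 + 5.911)/88 = 0.1768, SE = 0.0886, t = 0.1556/0.0886 = 1.755, p = 0.083. Removing one video-arm event in each case:

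| Patients | Before | p | After | p | Crosses 0.05? |
|---|---|---|---|---|---|
| 45/45 | 14 v 7 | 0.083 | 14 v 6 | 0.043 | yes |
| 45/45 | 13 v 7 | 0.131 | 13 v 6 | 0.072 | no |
| 47/46 | 14 v 7 | 0.095 | 14 v 6 | 0.0501 | no |
| 47/46 | 14 v 6 | 0.0501 | 14 v 5 | 0.024 | yes |
| 50/50 | 15 v 8 | 0.098 | 15 v 7 | 0.054 | no |

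Single examples can therefore be chosen to show either answer.

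**Step 4: how often it matters.** Treat the arms as independent binomials with 45 patients each and enumerate every pair of event counts. Sum the probability of pairs that are not significant in the video's favour but become so after one favourable change (one video event fewer or one control event more).

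| Video rate (control 30%) | Significant for video as observed | Made significant by one change |
|---|---|---|
| 10% | 68.5% | 11.0% |
| 15% | 39.8% | 12.3% |
| 20% | 18.8% | 8.6% |
| 30% (no effect) | 2.5% | 1.9% |

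With 46 per arm the last column reads 10.6%, 12.1%, 8.6% and 1.9%. With no effect, the chance of a false win for video goes from 2.5% to 2.5% + 1.9% = 4.4%, if one such change were made in every trial where it could count. These figures measure how fragile the result is. They do not estimate how often a reviewer would misclassify.

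**The case against.** The strongest reply is that the endpoint leaves study staff little to decide. It needs a laboratory-confirmed infection and fixed catheter-day criteria, and the contamination call is the hospital team's, made at the time of treatment. The abstractor mostly transcribes. This largely stands: a reader might infer that study staff can relabel unclear cultures as contaminants at will, and the definition does not allow that. What remains is event finding, timing, outside records, and notes with no clear call.

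A reader might also infer that the same open-label individuals run the questionnaires, know each patient's arm and then judge the outcome. The documents do not say so. They name a category of staff, not persons. The key is said to link code to identity, not to arm. Questionnaires go out electronically, and even in clinic the patient answers through a secure link, so staff need not see the replies. The supported statement is narrower: nothing prevents the abstractor from knowing the arm.

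Finally, a reader might infer that one reclassified event would reverse the trial's conclusion. Step 3 shows that this depends on the counts chosen, and by Fisher's exact test 14 v 7 moving to 14 v 6 of 45 goes only from 0.134 to 0.074. Sensitivity near p = 0.05 is common to small binary trials and is not in itself evidence of bias.

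**Conclusion.** The concern holds as a gap in protection of the primary endpoint. Study staff determine CRBSI status, and nothing in the protocol keeps the arm from them. The documents do not show that assessment is biased or that the assessors know the arm.

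Its size is moderate and confined to borderline results: about 9% to 12% of trials at video rates of 10% to 20%, and about 2% with no effect. This rests on a 30% control rate, 1:1 allocation, 45 analysed per arm, a two-sided 0.05 level and one change in the video's favour. The video-arm rates are assumptions. The point is worth correcting before the first one-year chart review, because it can be prevented cheaply and cannot be repaired afterwards.

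**What to change.** Add to Methodology:

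1. The one-year CRBSI abstraction is done by an existing team member who did not randomise that patient, issue the video link or collect that patient's questionnaires, working from a list that does not show the arm.
2. The allocation file is held separately and merged only after the CRBSI list is locked.
3. The treating team's documented contamination call is recorded as it stands, which the definition already requires. Cases where the call is absent or ambiguous are settled before unmasking.

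The cost is protocol wording, a separate allocation file and a split of roles among existing staff. It needs no extra reader, visit or procedure and does not change the sample size. Its limit is that the treating hospital team, which makes the contamination call, is not masked by this change, and the protocol does not say whether that team knows the arm.
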